Key Inclusion Criteria	
A subject may be enrolled in the study if all of the following inclusion criteria are met, provided no exclusion criteria are met:
 
 
1. Patients who are eligible for a WATCHMAN device according to current international and local guidelines (and future revisions) and per physician discretion;
 
2. Patients who are willing and capable of providing informed consent, participating in all testing associated with this clinical investigation at an approved clinical investigational center;
 
3. Patients whose age is 18 years or above, or of legal age to give informed consent specific to state and national law.
 
					
Key Exclusion Criteria	
Subjects will be excluded from the study if they meet any of the following criteria:
 
 
1. Patients who are currently enrolled in another investigational study or registry that would directly interfere with the current study, except when the patient is participating in a mandatory governmental registry, or a purely observational registry with no associated treatments. Each instance should be brought to the attention of the sponsor to determine eligibility.
 
2. Women of childbearing potential who are, or plan to become, pregnant during the time of the study (method of assessment upon physician's discretion);
 
					

EWOLUTION - REgistry on WATCHMAN Outcomes in Real-Life Utilization									
	3. The subject is unable or not willing to complete follow-up visits and examination for the duration of the study.								
Statistical Methods									
Statistical Test Method	No formal pre-specified hypotheses will be tested. However, a variety of statistical modeling methods may be utilized in order to assess associations between the likelihood of each of the three outcomes and the pre-specified patient and procedural characteristics, including multivariate logistic regression and classification and regression tree models.								

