## 7. Endpoint Analysis

Primary analyses may include, but will not be limited to, the following: procedural complications, incidence of stroke and death. Descriptive statistics will be used for baseline, procedure and follow-up data collected through the study.

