### **Attempt**

A subject who signs informed consent, meets eligibility criteria and has had the WATCHMAN Access Sheath inserted to implant the device, but eventually does not receive a WATCHMAN device will be classified as “**Attempt**”. These subjects may be withdrawn, unless a re-implant of a study device is planned, per physician discretion. These subjects will be handled as “Implant” (see next section), if the re-implant is successful. Subjects who eventually have not received a WATCHMAN device at the time of enrolment closure will remain classified as “Attempt” and be withdrawn. There are no FU requirements for Attempt subjects; however, adverse events will be collected up to the point of subject withdrawal. Attempt subjects count towards the enrolment ceiling and will be used for analyses of the endpoints. The original signed Informed Consent must be maintained in the center’s study file and the following forms must be completed:

- eCRFs in the “Baseline” and “Implant” folders
- “Adverse Event” forms for any adverse event that occurs after signing the Informed Consent, up to the point of subject withdrawal.
- “Patient Status” form for withdrawal, when applicable.

[figure not shown]
The date at which the patient status form has been completed will be the point of subject withdrawal.

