### 12.2. Statistical Analysis

Analysis will include all subjects enrolled into the study who undergo an attempted implant of the WATCHMAN device. While no formal hypothesis tests will be performed, descriptive statistics will be generated for the data collected at baseline, during the implant procedure and at follow-up. For continuous variables, the mean, standard deviation, median, range and 95% confidence intervals will be reported. Confidence intervals (95%) for the difference between means will be used to compare groups. For proportions, 95% confidence intervals will be reported. For time-to-event analyses, all subjects not having an event or lost to follow-up will be censored at the time of the last documented follow-up visit. Analyses may include, but will not be limited to, the following: procedural success, procedural complications, and incidence stroke/TIA.

A variety of methods may be utilized in order to assess associations between the likelihood of each of the three outcomes and the patient and procedural characteristics outlined below. Covariates will be chosen for inclusion in the models based on the number of patients with complete data for each outcome according to the prioritization in Table 4: Covariates of Interest.

Methods to model multivariate associations may include but are not limited to the following:

- Univariate analysis of individual predictors, and subsequent construction of multivariate logistic regression models incorporating all significant univariate predictors.
- Parsimonious multivariate logistic regression models constructed through stepwise selection algorithm.
- Classification and regression tree models.

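### The association models named for stroke/TIA ignore follow-up time, which is a modest fault; the larger one is significance-based covariate selection with few events

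*Combined protocol and SAP*

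**What the plan says.** Section 12.2 plans to relate patient and procedural characteristics to three outcomes. Its list is "procedural success, procedural complications, and incidence stroke/TIA". Section 7 and the synopsis list "procedural complications, incidence of stroke and death" instead, so it is unclear whether death is one of the three.

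The list of methods is open: "Methods to model multivariate associations may include but are not limited to the following". Three are named: univariate analysis followed by "subsequent construction of multivariate logistic regression models incorporating all significant univariate predictors", stepwise logistic regression, and classification and regression trees. The synopsis agrees, "including multivariate logistic regression and classification and regression tree models". No model that uses follow-up time is named.

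Covariates enter "based on the number of patients with complete data for each outcome according to the prioritization in Table 4: Covariates of Interest". No significance level, stepwise threshold, events-based limit or optimism check is given.

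One sentence in Section 12.2, confined to time-to-event analyses, says that "all subjects not having an event or lost to follow-up will be censored at the time of the last documented follow-up visit". It is attached to no named model or outcome. Section 10.3 adds, "There are no FU requirements for Attempt subjects", although these subjects are used in the endpoint analyses.

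**The concern.** Procedural success and procedural complications are settled at or near the implant, so a yes/no model fits them. Stroke/TIA and death accrue over time, and subjects are not all observed for the same time. Section 10.2 allows withdrawal and loss, Section 11.6 accepts a last visit at 24 ± 3 months, Section 12.1 allows early termination, and Attempt subjects may leave soon after the procedure. A logistic or tree model needs a rule for subjects with incomplete follow-up. Counting them as event-free and excluding them are both open under the present text, and they bias the odds ratio in opposite directions when a covariate is related to loss.

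The second issue does not depend on loss. When terms are kept because they reach significance and events are few, the terms kept are those whose estimates happened to be large. A registry report of predictors of stroke/TIA would then tend to overstate the effects it shows.

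**Working it through.** **1. The plan's own figure.** Table 3 assumes a 5% event rate. The half-width 1.96 × √(0.05 × 0.95 / N) is 1.91%, 1.56% and 1.35% at N = 500, 750 and 1000, which matches the stated 1.9%, 1.6% and 1.4%. The same inputs give 0.05 × 1000 = 50 events. The 5% is generic and not tied to stroke/TIA.

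**2. Events per term.** Table 4 has eight binary covariates and two with three levels: 8 + 2 × 2 = 12 terms. 50 / 12 = 4.2 events per term.

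**3. Incomplete follow-up.** The documents give no loss rate, and the following are assumptions: constant yearly hazards of stroke s = 0.025, death d = 0.06 and loss l = 0.05, over 2 years. Let h = s + d + l and F = 1 − exp(−2h).

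- Observed stroke proportion, lost counted as event-free: (s/h) × F.
- Lost stroke-free: (l/h) × F.
- Lost excluded: the first divided by (1 − the second).

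| Group | h | Event-free | Lost | Excluded |
|---|---|---|---|---|
| No loss | 0.085 | 0.0460 | 0 | 0.0460 |
| Reference, loss 5% | 0.135 | 0.0438 | 0.0876 | 0.0480 |
| Hazard ratio 1.5, loss 10% | 0.1975 | 0.0620 | 0.1652 | 0.0742 |
| Null covariate, loss 10% | 0.185 | 0.0418 | 0.1672 | 0.0502 |

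Odds ratios against the reference row:

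- True hazard ratio 1.5: (0.0620/0.9380) / (0.0438/0.9562) = 1.44 event-free; (0.0742/0.9258) / (0.0480/0.9520) = 1.59 excluded.
- Null covariate: 0.95 event-free, 1.05 excluded.
- Loss unrelated to the covariate: 1.52 and 1.00 under either handling.

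Range, with loss doubled by the covariate (hazard ratio 1.5 / null):

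- 2% a year: 1.49 / 0.98 event-free, 1.55 / 1.02 excluded.
- 10% a year: 1.37 / 0.91 event-free, 1.67 / 1.10 excluded.
- 5% a year with death at 3.2% a year (the first pivotal study's mortality figure in the Introduction, time unit assumed): still 1.44 / 0.95 and 1.59 / 1.05.

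**4. Size against noise.** With 50 events among 1000 subjects, 35% covariate prevalence (assumed) and a true odds ratio of 1.5, the standard error of the log odds ratio is about 0.298. For the null covariate, ln(1/0.952) / 0.298 = 0.165 and ln(1.047) / 0.298 = 0.154.

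**5. Visit window.** Last visits at 21 and 27 months, with no loss, give 0.0407 and 0.0512, an odds ratio of 1.27 for a null covariate if every event up to the last visit counts. This is an outer bound: it needs one covariate group seen entirely at 27 months and the other entirely at 21.

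**6. Would Cox recover the truth?** In simulation with last visits spread over 21 to 27 months, doubled loss, and Attempts at 3% without and 6% with the covariate (assumed), cause-specific Cox gave 1.503 and 0.998 for true values of 1.5 and 1.0. Logistic regression gave 1.40 / 0.92 event-free and 1.59 / 1.05 excluded.

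**7. Selection.** In 200,000 simulated two-by-two tables per setting, with a term kept at |z| > 1.96 (threshold assumed), 35% prevalence and a true odds ratio of 1.5:

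| Events | Kept | Geometric-mean odds ratio when kept |
|---|---|---|
| 25 | 17% | 2.8 |
| 50 | 28% | 2.1 |
| 75 | 39% | 1.9 |

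With 12 correlated terms resembling Table 4 and 50 events, a true odds ratio of 1.5 for previous stroke/TIA averaged 1.9 when kept by screening and 2.4 when kept stepwise. A pre-specified five-term model averaged 1.48; ridge on all 12 terms gave 1.19.

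**8. Optimism.** With two true odds ratios of 1.5, the median calibration slope was 0.32 screened, 0.28 stepwise, 0.38 pre-specified and 1.22 ridge. Apparent AUC was 0.61 to 0.63 against a true 0.53 to 0.54. Pre-specification removes the selection effect on the estimate but not the optimism.

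**The case against.** The strongest reply is that nothing commits the study to these models. They are optional, the list is open, no hypothesis is tested, and the sample size rests on precision of incidence. A survival model is therefore allowed already. That stands and limits the weight of the point, but a plan that names methods should name suitable ones for an outcome observed over time.

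The second reply is that the plan works to limit loss. Section 10.2 asks for at least three documented telephone attempts and a certified letter before a subject is called lost, and Section 11.6 uses telephone contact to capture endpoints. Table 2 treats a telephone contact as a follow-up visit, so the censoring rule can already be read to include it. Adverse events in Attempt subjects are collected up to a dated withdrawal. This also stands: loss may be low, and no document links loss or Attempt status to a Table 4 covariate.

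Third, Table 4 fixes the candidates and their priority. A reader might infer that covariates are chosen without any rule, or that the plan has no censoring rule at all. Neither is so. What is missing is a link from the censoring rule to a named model, and from the covariate rule to the number of events.

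Finally, the remedy has limits. Cox is also biased if loss depends on stroke beyond the modelled covariates, and ridge shrinks real effects.

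**Conclusion.** The point holds at moderate weight. For stroke/TIA, and death if retained, the named models ignore unequal follow-up, and the direction of any bias turns on a handling choice the plan leaves open. A reader might infer that the stroke/TIA associations would be badly wrong for this reason. The documents do not support that: they give no loss rate, and under the assumed 5% a year, doubled with the covariate, the shift is only about 0.15 to 0.17 standard errors, and absent if loss is unrelated to the covariate.

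Nor are descriptive results exempt. A simple 2-year stroke proportion of 4.60% without loss becomes 4.38% or 4.80% under the two handlings.

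Selection is the larger concern. With 4.2 events per candidate term, a true odds ratio of 1.5 is reported at about 2.1 on average when it survives screening. This rests on the generic 5%, an assumed p<0.05 and 35% prevalence; fewer events make it worse. Logistic regression and trees remain suitable for the procedural outcomes.

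**What to change.** In Section 12.2 and the synopsis:

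- For stroke/TIA, and death if retained, name cause-specific Cox models in place of logistic regression, and survival trees if trees are used. Censor at the last documented visit or telephone contact, at death for stroke/TIA, and at the withdrawal date for Attempt subjects without a follow-up visit.
- Keep logistic regression and ordinary trees for procedural success and procedural complications.
- Replace univariate-significance and stepwise selection with one of two options: a model pre-specified in Table 4 order, its size capped by the observed number of events under a rule stated before associations are examined, or a penalised model on the full Table 4 list. The second keeps the risk scores and anticoagulation type, which come late in the table.
- Report bootstrap optimism-corrected discrimination and calibration for either option.
- Use one outcome list in the synopsis, Section 7 and Section 12.2.

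The cost is SAP wording and some analysis time, with no new data. The downside is fewer covariates or shrunken effects, hazard ratios that need a cause-specific reading, and the remaining assumption that loss is independent of stroke given the modelled covariates.

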**Table 4: Covariates of Interest**

• Age $\geq$ 80 years
• Gender
• Type of AF (paroxysmal; persistent; permanent)
• Previous Stroke/TIA
• Previous major bleeding event
• HASBLED $\geq$ 3
• CHADS 2 $\geq$ 3

• CHA 2 DS 2 -VASc $\geq$ 5
• Type of anticoagulation therapy (Warfarin; NOACs; antiplatelet)
• Multiple concomitant procedures vs watchman implant only

## 13. Data Management

### 13.1. Data Collection, Processing, and Review

Subject data will be recorded in a limited access secure electronic data capture (EDC) system.

The clinical database will reside on a production server hosted by Medidata. All changes made to the clinical data will be captured in an electronic audit trail and available for review by Boston Scientific Corporation (BSC) or its representative. The associated RAVE software and database have been designed to meet regulatory compliance for deployment as part of a validated system compliant with laws and regulations applicable to the conduct of clinical studies pertaining to the use of electronic records and signatures. Database backups are performed regularly.

The Investigator provides his/her electronic signature on the appropriate electronic case report forms (eCRFs) in compliance with local regulations. A written signature on printouts of the eCRFs must also be provided if required by local regulation. Changes to data previously submitted to the sponsor require a new electronic signature by the Investigator acknowledging and approving the changes.

Visual and/or electronic data review will be performed to identify possible data discrepancies. Manual and/or automatic queries will be created in the EDC system and will be issued to the site for appropriate response. Site staff will be responsible for resolving all queries in the database in a timely manner.

### 13.2. Data Retention

The Investigator will maintain, at the investigative site, in original format all essential study documents and source documentation that support the data collected on the study subjects in compliance with ICH/GCP guidelines. Documents must be retained for at least 2 years after the last approval of a marketing application or until at least 2 years have elapsed since the formal discontinuation study. These documents will be retained for a longer period of time by agreement with BSC or in compliance with other local regulations. It is BSC's responsibility to inform the Investigator when these documents no longer need to be maintained. The Investigator will take measures to ensure that these essential documents are not accidentally damaged or destroyed. If for any reason the Investigator withdraws responsibility for maintaining these essential documents, custody must be transferred to an individual who will assume responsibility and BSC must receive written notification of this custodial change.

## 14. Amendments

If a protocol revision is necessary which affects the rights, safety or welfare of the subject or scientific integrity of the data, an amendment is required. Appropriate approvals (e.g., IRB/EC/FDA/CA) of the revised protocol must be obtained prior to implementation.

## 15. Deviations

An Investigator must not make any changes or deviate from this protocol, except to protect the life and physical well-being of a subject in an emergency. An investigator shall notify the sponsor and the reviewing IRB/EC of any deviation from the investigational plan to protect the life or physical well-being of a subject in an emergency, and those deviations which affect the scientific integrity of the clinical investigation.

All deviations from the investigational plan, with the reason for the deviation and the date of occurrence, must be documented and reported to the sponsor within 14 days using the appropriate EDC eCRF. Sites may also be required to report deviations to the IRB/EC, per local guidelines and government regulations.

Deviations will be reviewed and evaluated on an ongoing basis and, as necessary, appropriate corrective and preventive actions (including notification, center re-training, or discontinuation) will be put into place by the sponsor or its representatives.

## 16. Compliance

### 16.1. *Statement of Compliance*

This study will be conducted in accordance with ISO 14155:2011 Clinical Investigation of Medical Devices for Human Subjects-Good Clinical Practice, or the relevant parts of the ICH Guidelines for Good Clinical Practice, ethical principles that have their origins in the Declaration of Helsinki, and pertinent individual country laws and regulations. The study shall not begin until the required approval/favorable opinion from the Ethics Committee and/or regulatory authority has been obtained, if appropriate. Any additional requirements imposed by the EC or regulatory authority shall be followed, if appropriate.

### 16.2. *Investigator Responsibilities*

The Principal Investigator of an investigational center is responsible for ensuring that the study is conducted in accordance with the Clinical Study Agreement, the investigational plan/protocol, ISO 14155, ethical principles that have their origins in the Declaration of Helsinki, any conditions of approval imposed by the reviewing IRB/EC, and prevailing local and/or country laws and/or regulations, whichever affords the greater protection to the subject.

The Principal Investigator's responsibilities include, but are not limited to, the following.

- Prior to beginning the study, sign the Investigator Agreement and Protocol Signature page documenting his/her agreement to conduct the study in accordance with the protocol.
- Provide his/her qualifications and experience to assume responsibility for the proper conduct of the study and that of key members of the center team through up-to-date curriculum vitae or other relevant documentation and disclose potential conflicts of interest, including financial, that may interfere with the conduct of the clinical study or interpretation of results.
- Make no changes in or deviate from this protocol, except to protect the life and physical well-being of a subject in an emergency; document and explain any deviation from the approved protocol that occurred during the course of the clinical investigation.
- Create and maintain source documents throughout the clinical study and ensure their availability with direct access during monitoring visits or audits; ensure that all clinical-investigation-related records are retained per requirements.
- Ensure the accuracy, completeness, legibility, and timeliness of the data reported to the sponsor in the CRFs and in all required reports.
- Record, report, and assess (seriousness and relationship to the device/procedure) every adverse event and observed device deficiency.
- Report to BSC, per the protocol requirements, all SAEs and device deficiencies that could have led to a SADE.
- Report to the IRB/EC and regulatory authorities any SAEs and device deficiencies that could have led to a SADE, if required by the national regulations or this protocol or by the IRB/EC, and supply BSC with any additional requested information related to the safety reporting of a particular event.
- Allow the sponsor to perform monitoring and auditing activities, and be accessible to the monitor and respond to questions during monitoring visits.
- Allow and support regulatory authorities and the IRB/EC when performing auditing activities.
- Ensure that informed consent is obtained in accordance with applicable laws, this protocol and local IRB/EC requirements.
- Provide adequate medical care to a subject during and after a subject's participation in a clinical study in the case of adverse events, as described in the Informed Consent Form (ICF).
- Inform the subject of the nature and possible cause of any adverse events experienced.
- Inform the subject of any new significant findings occurring during the clinical investigation, including the need for additional medical care that may be required.

- Provide the subject with well-defined procedures for possible emergency situations related to the clinical study, and make the necessary arrangements for emergency treatment, Ensure that clinical medical records are clearly marked to indicate that the subject is enrolled in this clinical study.
- Ensure that, if appropriate, subjects enrolled in the clinical investigation are provided with some means of showing their participation in the clinical investigation, together with identification and compliance information for concomitant treatment measures (contact address and telephone numbers shall be provided).
- Inform, with the subject's approval or when required by national regulations, the subject's personal physician about the subject's participation in the clinical investigation.
- Make all reasonable efforts to ascertain the reason(s) for a subject's premature withdrawal from clinical investigation while fully respecting the subject's rights.
- Ensure that an adequate investigation site team and facilities exist and are maintained and documented during the clinical investigation.
- Ensure that maintenance and calibration of the equipment relevant for the assessment of the clinical investigation is appropriately performed and documented, where applicable.

